## **10.2. Patient consent**

As this study does not involve data subject to privacy laws according to applicable legal requirements, obtaining informed consent from patients by Pfizer is not required.

### **10.3. Institutional Review Board (IRB)/Independent Ethics Committee (IEC)**

There must be prospective approval of the study protocol, protocol amendments, and other relevant documents (e.g., informed consent forms if applicable) from the relevant IRBs/IECs. All correspondence with the IRB/IEC must be retained. Copies of IRB/IEC approvals must be forwarded to Pfizer.

Hence, the study will be submitted to institutional review board (IRB) of respective participating sites for methodological review or an independent ethics committee (IEC) for sites with no IRB. In addition, an IRB exemption will be sought on the basis that the study will collect only secondary data, no protected health information (PHI) will be collected and all data will be de-identified.

### **10.4 Ethical Conduct of the Study**

The study will be conducted in accordance with legal and regulatory requirements, as well as with scientific purpose, value and rigor and follow generally accepted research practices described in Guidelines for Good Pharmacoepidemiology Practices (GPP) issued by the International Society for Pharmacoepidemiology (ISPE).

## 11. MANAGEMENT AND REPORTING OF ADVERSE EVENTS/ADVERSE REACTIONS

This study protocol requires human review of patient-level unstructured data; unstructured data refer to verbatim medical data, including text-based descriptions and visual depictions of medical information, such as medical records, images of physician notes, neurological scans, X-rays, or narrative fields in a database. The reviewer is obligated to report adverse events (AE) with explicit attribution to any Pfizer drug that appear in the reviewed information (defined per the patient population and study period specified in the protocol). Explicit attribution is not inferred by a temporal relationship between drug administration and an AE, but must be based on a definite statement of causality by a healthcare provider linking drug administration to the AE.

The requirements for reporting safety events on the non-interventional study (NIS) adverse event monitoring (AEM) Report Form to Pfizer Safety are as follows:

- All serious and non-serious AEs with explicit attribution to **any Pfizer drug** that appear in the reviewed information must be recorded on the chart record form and reported, within 24 hours of awareness, to Pfizer Safety using the NIS AEM Report Form;
- Scenarios involving drug exposure, including exposure during pregnancy, exposure during breast feeding, medication error, overdose, misuse, extravasation, lack of efficacy and occupational exposure associated with the use of a Pfizer product must be reported, within 24 hours of awareness, to Pfizer Safety using the NIS AEM Report Form.

For these AEs with an explicit attribution or scenarios involving exposure to a Pfizer product, the safety information identified in the unstructured data reviewed is captured in the Event Narrative section of the report form, and constitutes all clinical information known regarding these AEs. No follow-up on related AEs will be conducted.

All the demographic fields on the NIS AEM Report Form may not necessarily be completed, as the form designates, since not all elements will be available due to privacy concerns with the use of secondary data sources. While not all demographic fields will be completed, at the very least, at least one patient identifier (eg, gender, age as captured in the narrative field of the form) will be reported on the NIS AEM Report Form, thus allowing the report to be considered a valid one in accordance with pharmacovigilance legislation. All identifiers will be limited to generalities, such as the statement “A 35-year-old female...” or “An elderly male...” Other identifiers will have been removed.

Additionally, the onset/start dates and stop dates for “Illness”, “Study Drug”, and “Drug Name” may be documented in month/year (mmm/yyyy) format rather than identifying the actual date of occurrence within the month/year of occurrence in the day/month/year (DD/MMM/YYYY) format.

All research staff members must complete the following Pfizer training requirements:

- *“Your reporting responsibility (YRR) Training for Vendors Working on Pfizer Studies (excluding interventional clinical studies and non-interventional primary data collection studies with sites/investigators)”.*

These trainings must be completed by research staff members prior to the start of data collection. All trainings include a “Confirmation of Training Certificate” (for signature by the trainee) as a record of completion of the training, which must be kept in a retrievable format. Copies of all signed training certificates must be provided to Pfizer.

Re-training must be completed on an annual basis using the most current Your Reporting Responsibilities training materials.

## **12. PLANS FOR DISSEMINATING AND COMMUNICATING STUDY RESULTS**

A comprehensive study report will be written on completion of study. The reports will incorporate methodology, sample, analyses, tables of results and summaries. All documents used throughout the study will be contained within the report as appendices. Results of this study may be submitted to conferences and journals for publication. As per Pfizer’s requirements, the project will only be considered complete upon delivery of the full study report and close of all study publications.

In the event of any prohibition or restriction imposed (e.g., clinical hold) by an applicable competent authority in any area of the world, or if the investigator is aware of any new information which might influence the evaluation of the benefits and risks of a Pfizer product, Pfizer should be informed immediately.

#### **15. LIST OF FIGURES**

None

#### **ANNEX 1. LIST OF STAND ALONE DOCUMENTS**

None

#### **ANNEX 2. ADDITIONAL INFORMATION**

Not applicable

1 AMENDMENTS FROM PREVIOUS VERSION(S)

Not Applicable

2 INTRODUCTION

This is a retrospective physician based medical record review study. will collect data from the medical records of patients, who have received palbociclib combination with aromatase inhibitor (as prescribed by the Physician) in menopausal state as initial endocrine therapy in MBC or with fulvestrant after progression on prior endocrine therapy will be reviewed. Data will be collected retrospectively at a single point in time from patient medical records.

This statistical analysis plan (SAP) will be the guiding document for the analyses that will be conducted in the study. This study intend to describe the demographics, clinical characteristics, treatment patterns, and clinical outcomes of adult female patients who have received palbociclib combination treatments for HR+/HER2- ABC/MBC in real world settings in India. SAP describes the data to be summarized and analyzed, including specifics of the statistical analyses to be performed.

This statistical analysis plan (SAP) is based on protocol version 1.0 dated 19th October 2020 and case report form (CRF) version 0.09, 20th May 2021.

2.1 STUDY DESIGN

This is a post marketing, retrospective, non-interventional study (NIS). The study will be conducted as a retrospective medical record review of patients who have received palbociclib combination with aromatase inhibitor (as prescribed by the Physician) in menopausal state as initial endocrine therapy in MBC or with fulvestrant after progression on prior endocrine therapy. It will comprise of an initial screening and eligibility assessment of patients followed by data collection from eligible patient records.

Data collection will be conducted using a predesigned electronic case report form (eCRF). Eligible physicians will be invited to complete the eCRF of patients that meet the study criteria. Patient eligibility will be confirmed by treating physicians. In order to allow for a sufficiently long observational window, treating physicians will be asked to go back to a specific point in time, the index date, and sequentially select the medical records of the next 'n' patients who meet the inclusion criteria.

Study population

Female cancer patients who have received palbociclib combination treatments for HR+/HER2- ABC/MBC in real world clinical practice setting.

Data source

Data will be collected from the Indian routine clinical practice settings. Approximately 10 oncologists will be included based on predefined egilbility criteria. Each selected physician will complete at least 10-15 electronic case report forms (eCRFs).

PFIZER CONFIDENTIAL

To be eligible, physicians must have treated or be treating 10 or more HR+/HER2-ABC/MBC patients who meet the eligibility criteria for the study. This will ensure that recruited physicians will be able to complete the minimum number of eCRFs required to participate in the study. In addition, during physician recruitment a representative geographical split and private/public practice split will be sought where possible to ensure a representative sample.

Inclusion Criteria

Physician inclusion criteria

- Oncologist.
- Responsible for treating ≥ 10 ABC/MBC patients who meet the eligibility criteria.
- Agrees to participate in the study and complete the eCRFs within the data collection period

Patients Inclusion Criteria

Patients must meet all of the following inclusion criteria to be eligible for inclusion in the study:

- ≥ 18 years old females.
- HR+/HER2- breast cancer diagnosis with confirmed metastatic or advanced disease.
- Received palbociclib with aromatase inhibitor (as prescribed by the Physician) as initial endocrine therapy in postmenopausal MBC patients or with fulvestrant in patients who have progressed on prior endocrine therapy.
- Patients on LHRH agonists for ovarian function suppression in pre- or perimenopausal stage only if prescribed palbociclib with fulvestrant.
- No prior or current enrolment in an interventional clinical trial for ABC/MBC.
- Minimum of 3 months of follow up data since palbociclib with fulvestrant initiation, or minimum of 6 months of follow up data since palbociclib with aromatase inhibitor initiation

Exclusion criteria

[figure not shown]
[figure not shown]
Patients meeting any of the following criteria will not be included in the study:

- Cancers other than breast cancer
- Male breast cancer
- Indications other than mentioned in the protocol
- Visceral crisis

Treatment/cohort labels

Palbociclib

PFIZER CONFIDENTIAL

2.2 STUDY OBJECTIVES

Primary Objectives:

1. To describe the demographics and clinical characteristics of patients who have received palbociclib combination with aromatase inhibitor (as prescribed by the Physician) in menopausal state as initial endocrine therapy in MBC or with fulvestrant after progression on prior endocrine therapy.
2. To summarize adjuvant therapies received for the treatment of early or locally advanced breast cancer (Stages 0-IIIa).
3. To describe treatments received in the advanced/metastatic setting, before and after palbociclib combination use.
4. To describe dosing and dose changes, interruptions, delays, and discontinuations associated with palbociclib use in clinical practice.
5. To describe supportive therapies received by patients while receiving palbociclib combination treatments.
6. To determine in overall population and defined subgroups, clinical outcomes including (but not limited to):
 - Proportion of patients who are progression free at specific intervals (eg, 6, 12, 18 months).
 - Objective response rate (ORR) - depending on availability of follow-up data.
 - Proportion of alive patients 1 and 2 years post palbociclib combination initiation -depending on availability of follow-up data (sample size permitting).

3 HYPOTHESES AND DECISION RULES

3.1 STATISTICAL HYPOTHESES

Not Applicable

3.2 STATISTICAL DECISION RULES

Not Applicable

4 ANALYSIS SETS/POPULATIONS

4.1 ALL SUBJECTS SET

All available data of 150 patients received palbociclib with aromatase inhibitor (as prescribed by the Physician) will be used for summary/analysis purpose.

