4.2 SAFETY ANALYSIS SET

The safety analysis set is the same as the all subjects set.

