5 ENDPOINTS AND COVARIATES**5.1 EFFICACY/EFFECTIVENESS ENDPOINT(S)**

- Treatment success of the patients treated with palbociclib with aromatase inhibitor (as prescribed by the Physician) will be progression free i.e. complete response, partial response or stable disease at the end of regimen.

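### SAP 4.1 and 5.1 restrict the All Subjects Set and the only listed effectiveness endpoint to aromatase-inhibitor patients, although the protocol and SAP section 2 also enrol palbociclib with fulvestrant

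*SAP*

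**What the plan says.** Two operative sentences of the SAP name only the aromatase inhibitor (AI):

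- The main analysis population, in 4.1, is defined thus: "All available data of 150 patients received palbociclib with aromatase inhibitor (as prescribed by the Physician) will be used for summary/analysis purpose".
- 5.1, effectiveness endpoint: "Treatment success of the patients treated with palbociclib with aromatase inhibitor (as prescribed by the Physician) will be progression free".

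The restriction carries further. On safety, SAP 4.2 says "The safety analysis set is the same as the all subjects set". Sections 4.3 (other sets), 4.4 (subgroups) and 5.2 (other endpoints) are all marked not applicable. Every table listed in SAP section 8 is labelled as All Subjects.

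SAP section 2 describes a wider population:

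- The introduction covers AI patients "or with fulvestrant after progression on prior endocrine therapy will be reviewed".
- The study population in 2.1 is "Female cancer patients who have received palbociclib combination treatments for HR+/HER2- ABC/MBC in real world clinical practice setting".
- The inclusion criteria in 2.1 admit AI "as initial endocrine therapy in postmenopausal MBC patients or with fulvestrant in patients who have progressed on prior endocrine therapy", and set a separate follow-up rule for the second group: "Minimum of 3 months of follow up data since palbociclib with fulvestrant initiation".
- Objective 1 in 2.2 covers AI "as initial endocrine therapy in MBC or with fulvestrant after progression on prior endocrine therapy".

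Protocol section 8 names the two combinations as the two populations of interest, and protocol 9.2.1 makes both eligible. Protocol 9.5 gives approximately 150 as the total for the study, without division by partner drug.

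**The concern.** The analysis-set definition decides who is counted, and here it conflicts with the population the study is designed to describe. A programmer who follows 4.1 to the letter would drop eligible fulvestrant patients from tables that claim to show all subjects, including the objective response rate (ORR) and clinical benefit rate in Table 11.

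The loss would not be even. Fulvestrant is eligible only after progression on earlier endocrine therapy. AI is eligible only as initial endocrine therapy for metastatic disease, so an AI patient could be second or later line only if her earlier metastatic lines were non-endocrine. The 11 tables by line of treatment would therefore lose most from the column for second and later lines. From 4.1 alone, a reader could not tell which population the results describe.

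**Working it through.** **1. Is 150 an AI-only count?** The city rows of protocol Table 2 give 20 + 10 + 40 + 20 + 10 + 10 + 20 + 20 = 150 records, from 1 + 1 + 2 + 2 + 1 + 1 + 1 + 1 = 10 physicians. The plan's figure is reproduced, and it is the whole-study total. It cannot also be the AI-only number if any fulvestrant patient is enrolled.

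**2. How many tables are affected?** SAP section 8 lists Tables 1 to 11 and 1.1 to 11.1: 11 + 11 = 22, all for All Subjects.

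**3. Does anything else in the SAP correct the wording?** The cohort label in 2.1 is simply palbociclib, the shell denominators refer to the palbociclib group, and 7.2 speaks of all patients. None of these is restricted by partner, but none amends the definition in 4.1. As far as they are visible, 7.2 and the shells name neither partner.

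**4. Could the restriction be deliberate?** Protocol 9.7 says that major changes to primary endpoint definitions or their analyses would be reflected in a protocol amendment. Protocol section 5 lists none, and the SAP says it is based on protocol version 1.0. The Table 1 shell also has a row for menopause induced by LHRH suppression, while the eligibility criteria admit pre- or perimenopausal patients on LHRH agonists only with fulvestrant. If eligibility is followed, an AI-only set would leave no such patients for that row. This points to an omission.

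**5. How many patients could be affected?** The documents give no split by partner. The nearest figure is the line mix of about 7:3 in protocol 9.1:

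- first line: 0.7 × 150 = 105
- second or later line: 0.3 × 150 = 45

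If every later-line patient and no first-line patient received fulvestrant, 45 of 150 (30%) would fall outside the set. Line is not the same as partner, so take a fulvestrant share p of 20% to 40% as an assumption.

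**6. Effect on ORR.** For all patients, ORR_all = (1 − p) × ORR_AI + p × ORR_F. Hence ORR_AI − ORR_all = p × (ORR_AI − ORR_F). With an illustrative 10-point difference between partners:

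| Assumed p | Patients outside the set | Shift in ORR (points) |
|---|---|---|
| 0.20 | 30 | 2 |
| 0.30 | 45 | 3 |
| 0.40 | 60 | 4 |

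**7. Effect on the later-line column.** If a share q of the roughly 45 later-line patients received fulvestrant (assumed), 45 × (1 − q) remain:

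| Assumed q | Later-line patients left |
|---|---|
| 0.5 | 22.5 (about 23) |
| 0.8 | 9 |
| 1.0 | 0 |

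The two ranges are separate illustrations. With q = 0.5 and no first-line fulvestrant use, the overall share is 22.5/150 = 15%. To reach 20% (30 patients), 7 or 8 first-line patients would also have to be on fulvestrant.

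**The case against.** The strongest reply is that nobody reading the whole SAP would apply 4.1 literally. The set is called All Subjects, its 150 is the whole-study total, section 2 states the population correctly, and Table 10 has rows for second, third and later lines. On that view this is a wording slip with no demonstrated effect on results. It is also fair to say that the sizes above rest on assumptions, that no listed table is a safety table, and that no visible shell has a row for treatment success. The consequences through 4.2 and 5.1 therefore cannot be traced to a visible output.

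Much of this stands. The slip is probably unintended, and the effects arise only under a literal reading. It does not remove the point. The SAP calls itself the guiding document for the analyses, and 4.1 is where it fixes the population. A reference to all patients in 7.2 is naturally read as all patients in the defined set. The same restriction appears twice, which makes a literal reading more plausible. Some text in 7.2 and the shells is redacted, but no redaction is visible in 4.1 or 5.1, and text elsewhere would still leave those sentences in conflict with section 2.

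**Conclusion.** The concern holds: SAP 4.1 and 5.1 are wrong as written, and no visible passage corrects them. The contradiction itself rests on the text and needs no assumption. Its practical size is conditional. If 4.1 is applied literally, all 22 tables lose the fulvestrant patients: about 45 of 150 if line stands in for partner, or 30 to 60 for an assumed share of 20% to 40%. The matching ORR shift is 2 to 4 points per 10-point difference between partners. If the analysts infer the intended population, the numbers do not change, but the SAP still misdescribes whom the tables cover. It should be fixed.

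**What to change.** - **SAP 4.1:** define the set as all available data from all eligible patients (approximately 150) who received palbociclib with either an aromatase inhibitor or fulvestrant. SAP 4.2 then follows without change.
- **SAP 5.1:** extend the population of the endpoint to patients treated with either combination.
- **If an AI-only analysis was in fact intended:** the SAP should say so and justify it, correct the 150, and reconcile the restriction with the protocol's objectives and its rule on amendments.

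The cost is two SAP sentences. The protocol already covers both regimens, so the rewording needs no amendment and no new data, and the set stays at about 150.

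Optionally, if the eCRF records the partner drug and redacted text does not already cover it, add a row for combination partner to Table 7 and show Table 11 by partner. Fulvestrant-only estimates would be imprecise. With about 45 patients and a true proportion of 50%, the 95% half-width is 1.96 × √(0.5 × 0.5 / 45) = 14.6 points, against 8.0 points with 150. The eCRF was not available, so whether this can be done is unknown.

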4.2 SAFETY ANALYSIS SET

The safety analysis set is the same as the all subjects set.

4.3 OTHER ANALYSIS SET

Not Applicable

4.4 SUBGROUPS

Not Applicable

5 ENDPOINTS AND COVARIATES**5.1 EFFICACY/EFFECTIVENESS ENDPOINT(S)**

- Treatment success of the patients treated with palbociclib with aromatase inhibitor (as prescribed by the Physician) will be progression free i.e. complete response, partial response or stable disease at the end of regimen.

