## **9.7 Data Analysis**

Detailed methodology for summary and statistical analyses of data collected in this study will be documented in a statistical analysis plan (SAP), which will be dated, filed and maintained by the sponsor. The SAP may modify the plans outlined in the protocol; any major modifications of primary endpoint definitions or their analyses would be reflected in a protocol amendment.

All analyses are to be descriptive and so all methods to be used will reflect this descriptive nature. The specific method that will be used depends on type of variable being analyzed and those methods are:

- Categorical variables – will be described using:
  - Number of observations (n);
  - Number and percent (%) within each category;
  - Number of missing observations.
- Numeric variables – will be described using:
  - Number of observations (n);
  - Mean & Standard deviation;
  - Minimum, Maximum, Median and 1st & 3rd Quartiles;
  - Number of missing observations.

PFIZER CONFIDENTIAL

- Time to event – will be described using:
  - A Kaplan-Meier chart that will visually estimate the distribution of times to some events, eg, progression, and will consider those patients for which the event has not yet occurred;
  - 1-year and 2-year rates, median or some more appropriate percentiles if the median time is not reached in the sample.

Missing data will be excluded on a case by case basis and will not be imputed. This will mean that each table will not necessarily be based on the same number of patients.

All statistical analyses will be conducted with general purpose statistical software (SAS) version 9.0 or higher

PFIZER CONFIDENTIAL

Palbociclib

A5481145, PD-0332991 NON-INTERVENTIONAL STUDY PROTOCOL

Final Protocol version 1.0, 19-Oct-2020

CCI

PFIZER CONFIDENTIAL

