5.2 OTHER ENDPOINTS

Not Applicable

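### SAP 5.1 judges progression-free status at the end of regimen, not at a fixed time since palbociclib initiation, so it cannot deliver the 6-, 12- and 18-month proportions in objective 6

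*SAP*

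**What the plan says.** SAP 5.1 defines treatment success as being "progression free i.e. complete response, partial response or stable disease at the end of regimen". The population is given in its opening words: "Treatment success of the patients treated with palbociclib with aromatase inhibitor (as prescribed by the Physician". The fulvestrant combination is not mentioned. SAP 5.2, on other endpoints, reads "Not Applicable", so 5.1 is the only endpoint in that section.

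SAP 2.2 repeats the protocol's objective 6: "To determine in overall population and defined subgroups, clinical outcomes including (but not limited to". The first outcome listed is "Proportion of patients who are progression free at specific intervals (eg, 6, 12, 18 months".

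Protocol 9.7 plans a Kaplan-Meier chart for time-to-event outcomes which "will consider those patients for which the event has not yet occurred", with 1-year and 2-year rates and the median. It lets the SAP modify the protocol's plans, but adds that "any major modifications of primary endpoint definitions or their analyses would be reflected in a protocol amendment". The SAP is based on protocol version 1.0, whose amendments section records none.

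Four other places bear on how 5.1 would be computed:

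- SAP 2: data are collected once, retrospectively.
- SAP 6: missing values are not imputed.
- SAP 7.1: unavailable data appear as a missing category, and denominators are whatever suits the analysis.
- Table 11, Note 1: percentages are based on all subjects in the palbociclib group.

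**The concern.** The term progression free carries a time in objective 6 and none in 5.1. Under 5.1 each patient is judged when her own regimen ends, whenever that is. The result then depends on why regimens ended, and says little about how long disease was controlled. A cohort with more early stops for toxicity or cost would show a higher success rate with the same disease course.

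Two further gaps follow from the wording. Some patients may still be on treatment when data are collected, since eligibility requires only 6 months of follow-up with an aromatase inhibitor and 3 with fulvestrant. Such patients have no end-of-regimen status, and 5.1 does not say how to class them. Read literally, 5.1 also leaves out the fulvestrant patients, whom objective 6 includes.

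At stake is a clinical outcome under a primary objective. A reader of the report could take the 5.1 figure for the progression-free proportion that the objectives promise.

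**Working it through.** The plan gives no figure for this endpoint, so there is none to reproduce. The check compares the definitions and then adds an illustration of size.

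**Definitions side by side**

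| | Objective 6 | Protocol 9.7 | SAP 5.1 |
|---|---|---|---|
| Time | Fixed intervals, eg 6, 12, 18 months | Time to event; 1- and 2-year rates, median | End of each patient's regimen |
| Patients | Overall and subgroups | No restriction stated | Aromatase-inhibitor patients named |
| No event yet | Not stated | Taken into account | Not stated |

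**Two patients.** Patient A stops for toxicity at month 1 with stable disease. Under 5.1 she is a success, although nothing is yet known about her at month 6. Patient B progresses at month 30. Under 5.1 she is a failure, although she was progression free at 6, 12 and 18 months. For both, 5.1 gives the wrong answer to the question in objective 6.

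**Inputs to the illustration**

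- Median progression-free survival of 24.8 months, cited in protocol section 7 for palbociclib with letrozole.
- Exponential times (assumption).
- A constant rate of stopping without progression, 0.0025 to 0.02 per month, independent of progression (assumption; the documents give no rate).
- A regimen ends only through a progression-free-survival event or such a stop (simplification).

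**Fixed-time proportions**

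- Event rate: h_prog = ln 2 / 24.8 = 0.02795 per month.
- S(t) = exp(-h_prog × t).
- S(6) = exp(-0.1677) = 0.846.
- S(12) = exp(-0.3354) = 0.715.
- S(18) = exp(-0.5031) = 0.605.

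The stop rate does not enter these values. Under the independence assumption, Kaplan-Meier with stopped patients censored estimates the same quantities.

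**Success under 5.1, among patients whose regimen has ended**

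By follow-up F, the probability of having stopped without progression is [h_stop / (h_stop + h_prog)] × [1 - exp(-(h_stop + h_prog) × F)]. The second factor is the probability that the regimen has ended at all. Dividing by it leaves h_stop / (h_stop + h_prog), and F drops out.

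- h_stop = 0.0025: 0.0025 / 0.03045 = 0.082.
- h_stop = 0.01: 0.01 / 0.03795 = 0.264.
- h_stop = 0.02: 0.02 / 0.04795 = 0.417.

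Progression is identical in all three rows, yet success rises from 8% to 42%, and follow-up time has no effect on it.

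**Patients still on treatment.** With h_stop = 0.01 and 24 months of follow-up for everyone (assumed), exp(-0.03795 × 24) = 0.402 are still on treatment. Success is then (1 - 0.402) × 0.264 = 0.158 if they stay in the denominator as missing, and 0.264 if they are left out. How 5.1 classes them therefore matters.

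**The case against.** The strongest reply is that 5.1 does not claim to implement the 6-, 12- and 18-month item. It defines treatment success, objective 6 is an open list with the months given as examples, and protocol 9.7 already covers progression over time. That stands to this extent: an additional descriptive outcome is allowed. But 5.1 explicitly equates its outcome with being progression free and is the only endpoint in SAP section 5. The term would then have two meanings in one report.

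A reader might infer that the plan contains no timed analysis. The documents do not support that. Text is redacted after protocol 9.7, around the Clinical Outcome part of SAP 7.2, and within and after Table 11. The visible outcome rows use the initially recorded response in all patients, which is a different assessment from 5.1. That is a mismatch with 5.1, and it is not proof of a gap.

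A reader might also infer that an analyst may freely count patients still on treatment as failures, drop them or count them as successes. The text does not treat these choices equally. The missing-category rule, the bar on imputation and Table 11 Note 1 lean towards keeping them in the denominator as missing. Nothing visible supports counting them as successes. Still, no text says that ongoing treatment is to be treated as missing data.

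Finally, the aromatase-inhibitor wording may not be a deliberate exclusion. SAP 4.1 describes the whole analysis set in the same way, "All available data of 150 patients received palbociclib with aromatase inhibitor (as prescribed by the Physician", so it may be carried over.

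**Conclusion.** The point holds as a defect in the legible definition in SAP 5.1. An outcome judged at end of regimen has no fixed time since palbociclib initiation. It rises with non-progression stops even when progression is unchanged, and it cannot yield the proportions in objective 6. It also departs from the time-to-event approach in protocol 9.7 with no amendment recorded. If a redacted section does hold a timed analysis, 5.1 still gives progression free a second, conflicting meaning.

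The contrast of 84.6%, 71.5% and 60.5% with about 8% to 42% shows direction and scale only. It rests on exponential times, a trial median applied to a routine-practice cohort, and stop rates that are not in the documents. It does not predict this study's results. The comparison of definitions needs none of these assumptions.

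This should be fixed before the analysis. The study is descriptive with no hypothesis test, so the harm is a misread or irreproducible descriptive figure under a primary objective.

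**What to change.** - Restate SAP 5.1, for both combinations, as time from palbociclib initiation to first recorded progression or death.
- Censor patients without an event, including those still on treatment, at last assessment. State a rule for patients who start new anticancer therapy before progression. Without that rule, patients who stop with stable disease could still be handled in different ways.
- Report Kaplan-Meier proportions at 6, 12 and 18 months, as objective 6 asks, besides the 1-year and 2-year rates and median already in protocol 9.7. Show them overall and by line of treatment.
- Keep end-of-regimen response as a separately named descriptive item, with patients still on treatment shown as their own category.
- Align any redacted time-to-event text with this definition.

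The cost is SAP wording and a few standard survival outputs. The analysis relies on progression and last-assessment dates, which the PFS and TTP outcomes in protocol Table 1 already need. The eCRF is not among the documents, so whether it collects those dates should be confirmed.
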